10.1 Definition of adverse events and reporting requirements

10.1.1 Adverse events

An adverse event (AE) is any untoward medical occurrence (e.g. any unfavorable and unintended sign [including abnormal laboratory findings], symptom or disease) in a clinical

investigation participant after providing written informed consent for participation in the study. Therefore, an AE may or may not be temporally or causally associated with the use of a medicinal (investigational) product.

The investigator has the responsibility for managing the safety of individual participant and identifying adverse events.

Novartis qualified medical personnel will be readily available to advise on trial related medical questions or problems.

The occurrence of adverse events must be sought by non-directive questioning of the participant at each visit during the study. Adverse events also may be detected when they are volunteered by the participant during or between visits or through physical examination findings, laboratory test findings, or other assessments.

Adverse events must be recorded under the signs, symptoms, or diagnosis associated with them, accompanied by the following information (as far as possible) (if the event is serious refer to [Section 10.1.2](#)):

1. The severity grade:
 - mild: usually transient in nature and generally not interfering with normal activities
 - moderate: sufficiently discomforting to interfere with normal activities
 - severe: prevents normal activities
2. Its relationship to the study treatment. If the event is due to lack of efficacy or progression of underlying illness (i.e. progression of the study indication) the assessment of causality will usually be 'Not suspected.' The rationale for this guidance is that the symptoms of a lack of efficacy or progression of underlying illness are not caused by the trial drug, they happen in spite of its administration and/or both lack of efficacy and progression of underlying disease can only be evaluated meaningfully by an analysis of cohorts, not on a single participant
3. Its duration (start and end dates) or if the event is ongoing, an outcome of not recovered/not resolved must be reported
4. Whether it constitutes a SAE (see [Section 10.1.2](#) for definition of SAE) and which seriousness criteria have been met
5. Action taken regarding with study treatment.

All adverse events must be treated appropriately. Treatment may include one or more of the following:

- Dose not changed
 - Dose Reduced/increased
 - Drug interrupted/withdrawn
6. Its outcome

Conditions that were already present at the time of informed consent should be recorded in medical history of the participant.

Adverse events (including lab abnormalities that constitute AEs) should be described using a diagnosis whenever possible, rather than individual underlying signs and symptoms.

Adverse event monitoring should be continued for at least 30 days following the last dose of study treatment.

Once an adverse event is detected, it must be followed until its resolution or until it is judged to be permanent (e.g. continuing at the end of the study), and assessment must be made at each visit (or more frequently, if necessary) of any changes in severity, the suspected relationship to the interventions required to treat it, and the outcome.

Information about adverse drug reactions for the investigational drug can be found in the Investigator's Brochure (IB).

Abnormal laboratory values or test results constitute adverse events only if they fulfill at least one of the following criteria:

- they induce clinical signs or symptoms
- they are considered clinically significant
- they require therapy

Clinically significant abnormal laboratory values or test results must be identified through a review of values outside of normal ranges/clinically notable ranges, significant changes from baseline or the previous visit, or values which are considered to be non-typical in participant with the underlying disease.

10.1.2 Serious adverse events

An SAE is defined as any adverse event [appearance of (or worsening of any pre-existing)] undesirable sign(s), symptom(s), or medical condition(s) which meets any one of the following criteria:

- fatal
- life-threatening

Life-threatening in the context of a SAE refers to a reaction in which the participant was at risk of death at the time of the reaction; it does not refer to a reaction that hypothetically might have caused death if it were more severe (please refer to the ICH-E2D Guidelines).

- results in persistent or significant disability/incapacity
- constitutes a congenital anomaly/birth defect
- requires inpatient hospitalization or prolongation of existing hospitalization, unless hospitalization is for:
 - routine treatment or monitoring of the studied indication, not associated with any deterioration in condition
 - elective or pre-planned treatment for a pre-existing condition that is unrelated to the indication under study and has not worsened since signing the informed consent
 - social reasons and respite care in the absence of any deterioration in the participant's general condition
 - treatment on an emergency outpatient basis for an event not fulfilling any of the definitions of a SAE given above and not resulting in hospital admission

- is medically significant, e.g. defined as an event that jeopardizes the participant or may require medical or surgical intervention to prevent one of the outcomes listed above

Medical and scientific judgment should be exercised in deciding whether other situations should be considered serious reactions, such as important medical events that might not be immediately life threatening or result in death or hospitalization but might jeopardize the participant or might require intervention to prevent one of the other outcomes listed above. Such events should be considered as “medically significant.” Examples of such events are intensive treatment in an emergency room or at home for allergic bronchospasm, blood dyscrasias, or convulsions that do not result in hospitalization or development of dependency or abuse (please refer to the ICH-E2D Guidelines)).

All new malignant neoplasms will be assessed as serious under “medically significant” if other seriousness criteria are not met.

Any suspected transmission via a medicinal product of an infectious agent is also considered a serious adverse reaction.

10.1.3 SAE reporting

To ensure participant safety, every SAE, regardless of causality, occurring after the participant has provided informed consent and until 30 days after the last study visit must be reported to Novartis safety immediately, without undue delay, under no circumstances later than within 24 hours of obtaining knowledge of the events (Note: If more stringent, local regulations regarding reporting timelines prevail). Detailed instructions regarding the submission process and requirements are to be found in the investigator folder provided to each site.

All follow-up information for the SAE including information on complications, progression of the initial SAE and recurrent episodes must be reported as follow-up to the original episode immediately, without undue delay, but under no circumstances later than within 24 hours of the investigator receiving the follow-up information (Note: If more stringent, local regulations regarding reporting timelines prevail). An SAE occurring at a different time interval or otherwise considered completely unrelated to a previously reported one must be reported separately as a new event.

If the SAE is not previously documented in the Investigator’s Brochure or Package Insert (new occurrence) and is thought to be related to the study treatment, a CMO & PS Department associate may urgently require further information from the investigator for health authority reporting. Novartis may need to issue an Investigator Notification (IN) to inform all investigators involved in any study with the same study treatment that this SAE has been reported.

Suspected Unexpected Serious Adverse Reactions (SUSARs) will be collected and reported to the competent authorities and relevant ethics committees in accordance with EU Guidance 2011/C 172/01 or as per national regulatory requirements in participating countries.

Any SAEs experienced after the 30 day period after the last study visit should only be reported to Novartis Safety if the investigator suspects a causal relationship to study treatment.

10.1.4 Pregnancy reporting

Pregnancies

If a female trial participant becomes pregnant, the study treatment should be stopped, and the trial participant must be asked to read and sign pregnancy consent form to allow the Study Doctor ask about her pregnancy. To ensure participant safety, each pregnancy occurring after signing the informed consent must be reported to Novartis within 24 hours of learning of its occurrence. The pregnancy should be followed up until birth and one year after childbirth to determine outcome, including spontaneous or voluntary termination, details of the birth, and the presence or absence of any birth defects, congenital abnormalities, or maternal and/or newborn complications.

Pregnancy should be recorded and reported by the investigator to the Novartis Chief Medical Office and Patient Safety (CMO&PS). Pregnancy follow-up should be recorded on the same form and should include an assessment of the possible relationship to the study treatment with any pregnancy outcome. Any SAE experienced during pregnancy must be reported.

10.1.5 Reporting of study treatment errors including misuse/abuse

Medication errors are unintentional errors in the prescribing, dispensing, administration or monitoring of a medicine while under the control of a healthcare professional, participant or consumer (EMA definition).

Study treatment errors and uses outside of what is foreseen in the protocol will be recorded on the appropriate CRF irrespective of whether or not associated with an AE/SAE and reported to Safety only if associated with an SAE. Misuse or abuse will be collected and reported in the safety database irrespective of it being associated with an AE/SAE within 24 hours of Investigator's awareness.

Table 10-1 Guidance for capturing the study treatment errors including misuse/abuse

Treatment error type	Document in Dosing CRF (Yes/No)	Document in AE eCRF	Complete SAE form
Unintentional study treatment error	Yes	No	No

For more information on AE and SAE definition and reporting requirements, please see the respective sections.

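### Section 10.1.5 contradicts itself on treatment errors associated with an SAE: the text sends them to Safety, while Table 10-1 says without condition that no SAE form is completed

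*Protocol*

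**What the plan says.** The text of Protocol section 10.1.5 sets two rules for study treatment errors. They "will be recorded on the appropriate CRF irrespective of whether or not associated with an AE/SAE", and they are "reported to Safety only if associated with an SAE". It treats misuse and abuse separately: "Misuse or abuse will be collected and reported in the safety database irrespective of it being associated with an AE/SAE", within 24 hours of the investigator becoming aware.

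Table 10-1 then gives sites a guide to capturing errors. Its row "Unintentional study treatment error" reads Yes for the dosing CRF, No for the AE eCRF and No for the SAE form, with no condition or footnote. The line under the table reads "For more information on AE and SAE definition and reporting requirements, please see the respective sections".

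The general rules make no exception for treatment errors. Section 10.1.3 requires reporting within 24 hours of "every SAE, regardless of causality, occurring after the participant has provided informed consent and until 30 days after the last study visit". Section 10.1.1 requires AEs to be recorded, section 6.7.2 requires any AE to be entered in the eCRF, and Table 8-2 requires clinically significant slit-lamp or ophthalmoscopy findings to be entered as AEs.

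**The concern.** The text and the table give different instructions for the same situation, an unintentional error with an associated SAE. The table is the part laid out as a quick guide, so a busy site may well use it alone.

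Injection timing is a safety matter in this trial. Sections 1.1 and 4.5 say that the interval should not fall below 8 weeks after loading, because more intraocular inflammation, retinal vasculitis and retinal vascular occlusion were seen with 4-weekly dosing. SAP Table 5-1 lists over-treatment and a wrongly adjusted treatment interval among its deviations, so the sponsor foresees such errors. SAP section 2.7.1.1 builds the tables of adverse events of special interest by mapping reported AEs, so an event never entered as an AE cannot appear in them. Two things are at stake: whether Safety learns that an SAE followed a treatment error, and whether a linked event could be left out of the AE record.

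**Working it through.** No arithmetic applies. The check compares each cell of the Table 10-1 row with the text above it and with the general rules.

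| Cell | Table 10-1 | Text of 10.1.5 | Other sections | Result |
|---|---|---|---|---|
| Dosing CRF | Yes | Always recorded on the appropriate CRF | 6.6.1: schedule deviations are captured on the dispensing form | Consistent |
| AE eCRF | No | AE eCRF not named | 10.1.1 and 6.7.2: AEs are recorded | Consistent with the text above; conflicts with 10.1.1 and 6.7.2 if an AE follows |
| SAE form | No | Report to Safety if an SAE is associated | 10.1.3: every SAE is reported | Conflicts with both if an SAE is associated |

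Three cases show where the conflict lies:

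1. **Error with no event.** Text and table agree: dosing CRF only, nothing to Safety.
2. **Error followed by a non-serious AE.** The text of 10.1.5 asks for no report to Safety, and neither does the table. The AE itself must be recorded under 10.1.1 and 6.7.2, but the AE eCRF cell says No.
3. **Error associated with an SAE.** The text requires a report to Safety, and 10.1.3 requires the SAE to be reported. The SAE form cell says No.

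Suppose next that the row describes the error alone and not what follows from it. Case 2 is then resolved, because an error is not itself an AE and the AE is recorded under its own rule. Case 3 is not resolved, because the text makes the error itself reportable when an SAE is associated. Section 10.1.3 brings the SAE to Safety but does not ask for the error to be reported with it. The line under the table points to the AE and SAE rules and does not supply the missing condition.

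One assumption is needed: that the SAE form is the site's route to Safety. Section 10.1.5 names no other route, and 10.1.3 leaves the submission details to the investigator folder.

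**The case against.** The strongest reply is that Table 10-1 is about capturing errors, that an error without harm is neither an AE nor an SAE, and that No/No is then correct. The line below the table sends the reader elsewhere for AE and SAE reporting. Event capture is also required in several places: sections 6.7.2, 10.1.1 and 10.1.3, Table 8-2, the examination and imaging rules for suspected inflammation in section 10, and the monitoring check of SAE documentation in section 11.3. For a vasculitis or occlusion case to be lost, a site would have to let one table override all of these.

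Most of this stands. It removes any claim that the plan lacks AE capture, and it leaves the AE cell as an ambiguity. It does not rescue the SAE form cell, for the reason given under case 3.

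A reader might go further and infer a sizeable bias in the safety tables. Applying the 4-weekly rates quoted in section 4.2 (vasculitis 0.8%, occlusion 2.0%) to 250 participants gives 0.008 × 250 = 2 and 0.020 × 250 = 5 cases, so one missed case would be 1/5 to 1/2 of the count. The documents do not support this as a measure of the defect. The rates come from a regimen that this trial excludes. The calculation uses all participants, although only those with an event after an error, at a site that misreads the table, are relevant. It also assumes the missed case that it sets out to show.

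A reader might also infer that a misuse/abuse row was omitted, since the table title covers misuse and abuse. The text available for this review was extracted from a PDF and may have lost a row, and the 24-hour rule is in the text in any case.

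**Conclusion.** The point holds as an internal inconsistency in a site instruction. The SAE form cell of Table 10-1 contradicts the sentence above it whenever an SAE is associated with the error. The AE eCRF cell, read literally for an error followed by an AE, conflicts with sections 10.1.1 and 6.7.2, but not with the sentence above it.

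The consequence is a risk of misreading: a site relying on the table may not report the error with its SAE, or may omit the linked event. The size of that risk cannot be estimated, because the documents give neither the frequency of treatment errors nor the chance that a site follows the table over the other sections. No endpoint or planned analysis is shown to be affected. It is still worth correcting, because the table as written gives a wrong safety-reporting instruction and the correction is nearly free.

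**What to change.** By amendment, do one of the following in Table 10-1:

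- Change the AE eCRF cell to: only if associated with an AE. Change the SAE form cell to: only if associated with an SAE.
- Keep the cells and add a footnote: the row refers to the error itself; any resulting AE or SAE follows sections 10.1.1 to 10.1.3; an error associated with an SAE is reported to Safety.

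While doing so, check the source table for a misuse/abuse row and, if there is none, consider adding one that repeats the 24-hour rule in the text.

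The cost is two cells or one footnote, which can go into the next amendment. Section 14.1 requires a written amendment for protocol changes, so a site letter alone would not correct the table. No analysis, sample size or data collection form needs to change.

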10.2 Additional Safety Monitoring

Not applicable.

11 Data Collection and Database management

11.1 Data collection

All data should be recorded, handled, and stored in a way that allows its accurate reporting, interpretation, and verification.

Designated investigator staff will enter the data required by the protocol into the Electronic Case Report Forms (eCRF). The eCRFs have been built using fully validated secure web-enabled software that conforms to 21 CFR Part 11 requirements, Investigator site staff will not be given access to the EDC system until they have been trained. Automatic validation programs check for data discrepancies in the eCRFs, allow modification and/or verification of the entered data by the investigator staff.

The investigator/designee is responsible for assuring that the data entered into eCRF is complete, accurate, and that entry and updates are performed in a timely manner. The Investigator must certify that the data entered are complete and accurate.

After final database lock, the investigator will receive copies of the participant data for archiving at the investigational site.

11.2 Database management and quality control

Novartis personnel (or designated CRO) will review the data entered by investigational staff for completeness and accuracy. Electronic data queries stating the nature of the problem and requesting clarification will be created for discrepancies and missing values and sent to the investigational site via the EDC system. Designated investigator site staff are required to respond promptly to queries and to make any necessary changes to the data.

Concomitant treatments and prior medications entered into the database will be coded using the World Health Organization (WHO) Drug Reference List, which employs the Anatomical Therapeutic Chemical classification system. Medical history/current medical conditions and adverse events will be coded using the Medical Dictionary for Regulatory Activities (MedDRA) terminology.

Dates of visits and data about study treatments dispensed to the participant, will be tracked using an Interactive Response Technology (IRT). The system will be supplied by a vendor, who will also manage the database. The data will be sent electronically to Novartis (or a designated CRO) at specific timelines.

Once all the necessary actions have been completed and the database has been declared to be complete and accurate, it will be locked and made available for data analysis. Any changes to the database after that time can only be made after written agreement by Novartis development management.

11.3 Site monitoring

Before study initiation, at a site initiation visit or at an investigator's meeting, a Novartis/delegated CRO representative will review the protocol and data capture requirements (i.e. eCRFs) with the investigators and their staff. During the study, Novartis employs several methods of ensuring protocol and GCP compliance and the quality/integrity of the sites' data. The field monitor will visit the site to check the completeness of participant records, the accuracy of data capture / data entry, the adherence to the protocol and to Good Clinical Practice, the progress of enrollment, and to ensure that study treatment is being stored, dispensed, and accounted for according to specifications. Key study personnel must be available to assist the field monitor during these visits. Continuous remote monitoring of each site's data

may be performed by a centralized Novartis/delegated CRO/CRA organization. Additionally, a central analytics organization may analyze data & identify risks & trends for site operational parameters, and provide reports to Novartis clinical teams to assist with trial oversight.

The investigator must maintain source documents for each participant in the study, consisting of case and visit notes (hospital or clinic medical records) containing demographic and medical information, laboratory data, electrocardiograms, and the results of any other tests or assessments. All information on CRFs must be traceable to these source documents in the participant's file. The investigator must also keep the original informed consent form signed by the participant (a signed copy is given to the participant).

The investigator must give the monitor access to all relevant source documents to confirm their consistency with the data capture and/or data entry. Novartis monitoring standards require full verification for the presence of informed consent, adherence to the inclusion/exclusion criteria, documentation of SAEs, and of data that will be used for all primary variables. Additional checks of the consistency of the source data with the CRFs are performed according to the study-specific monitoring plan. No information in source documents about the identity of the participants will be disclosed.

12 Data analysis and statistical methods

Any data analysis carried out independently by the investigator should be submitted to Novartis before publication or presentation.

Continuous variables will be summarized for the measured values at each visit and change from the baseline values using the number of observations, mean, standard deviation, quartiles, minimum and maximum. Categorical variables will be summarized with counts and percent in each category. Endpoints characterizing TtC regimen will be presented together with two-sided 95% Confidence Intervals (CI). When appropriate, two-sided p-values will be presented as a descriptive statistics.

All the endpoints, including the primary endpoint, are defined with respect to the study eye.

Additional analysis may be also conducted to evaluate the impact of the COVID-19 pandemic and the urgent safety measure.

In addition to the statistical methods outlined below, further details will be described in the statistical analyses plan (SAP).

